Guidelines for study treatment temporary discontinuations, including delays and interruptions, and permanent discontinuations for toxicity are outlined in [Table 2](#).

Any patient currently receiving cemiplimab who was previously treated with a phosphatidylinositol 3-kinase (PI 3-K) inhibitor and who develops stomatitis or mucositis should temporarily suspend study treatment. If this or any other immune-related AE occurs among these patients, the sponsor should be informed as soon as possible to discuss further management of the patient. An irAE of any grade in a patient previously treated with a PI 3-K inhibitor should be reported as an adverse event of special interest (AESI).

Table 2: Study Treatment Dose Modifications or Discontinuations

Toxicity	Grade	Hold Treatment?	Restarting Criteria	Restarting Dose/Schedule	Discontinuation Criteria
Hematological Toxicity (other than grade 3 thrombocytopenia greater than 7 days or associated with bleeding)	1, 2, 3	No	N/A	N/A	N/A
	4	Yes	Toxicity resolves to grade \leq 1 or baseline	Decrease cemiplimab dosage to the next lower dosing level (see Table 1)	Toxicity does not resolve within 84 days of last infusion Permanent discontinuation should be considered for any severe or life-threatening event
Grade 3 thrombocytopenia greater than 7 days or associated with bleeding	3	Yes	Toxicity resolves to grade \leq 1 or baseline	Decrease cemiplimab dosage to the next lower dosing level (see Table 1)	Toxicity does not resolve within 84 days of last infusion Permanent discontinuation should be considered for any severe or life-threatening event
Nonhematological Toxicity Note: Exceptions to be treated as for Grade 1 toxicity: 
Grade 2 alopeciaGrade 2 fatigueClinically insignificant lab abnormality not meeting AE criteria	1	No	N/A	N/A	N/A
	2	Consider withholding for persistent symptoms	Toxicity resolves to grade 0–1 or baseline	Clinical AE resolves within 4 weeks: Same dose and schedule Clinical AE does not resolve within 4 weeks: May decrease cemiplimab dosage to the next lower dosing level (see Table 1)	Toxicity does not resolve within 84 days of last infusion
	3	Yes	Toxicity resolves to grade 0–1 or baseline	Decrease cemiplimab dosage to the next lower dosing level (see Table 1)	Toxicity does not resolve within 84 days of last infusion
	4	Yes	N/A	N/A	Patient must be discontinued

AE=adverse event, N/A=not applicable

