For additional information regarding AEs with a potential for irAEs, reference [Table 3](#) and [Appendix 3](#).

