7.3.2.1. Immune-Related Adverse Events

Case report forms (CRFs) for this study are designed to capture AEs that may be suggestive of potential irAEs. Attribution of AEs in the CRFs will require not only the investigator's assessment

regarding whether or not the AE was related to cemiplimab, but also whether or not the AE was an irAE. Please see the CRF completion guidelines for information about attribution of irAEs.

Investigators must be extremely vigilant and be ready to intervene early in the management of irAEs, as the onset of symptoms of irAEs (eg, pneumonitis or endocrinopathies) may be subtle. Detailed guidance of management of irAEs is provided in [Appendix 3](#). In the event of irAEs that are not addressed in [Appendix 3](#), general guidance is provided in [Table 3](#). The recommendations in [Table 3](#) and [Appendix 3](#) should be seen as guidelines, and the treating physician should exercise clinical judgment based on the symptoms and condition of the individual patient.

Table 3: General Treatment Hold Guidelines for Immune-Related Adverse Events

Severity	Withhold/Discontinue Treatment?	Supportive Care
Grade 1	No action	Provide symptomatic treatment
Grade 2	May withhold treatment	Consider systemic corticosteroids in addition to appropriate symptomatic treatment
Grade 3 Grade 4	Withhold treatment Discontinue if unable to reduce corticosteroid dose to <10 mg per day prednisone equivalent within 12 weeks of toxicity	Systemic corticosteroids are indicated in addition to appropriate symptomatic treatment. May utilize 1 to 2 mg/kg prednisone or equivalent per day. Steroid taper should be considered once symptoms improve to Grade 1 or less and tapered over at least 4 weeks. For any severe (Grade 3-4) irAE, if symptoms worsen or do not improve on adequate corticosteroids within 48 to 72 hours, consider adding additional immunosuppressive agents (to be selected from agents such as infliximab, cyclophosphamide, cyclosporine, mycophenolate mofetil). Referral of the patient to a specialized unit for assessment and treatment should be considered.

Note: These recommendations should be seen as guidelines, and the treating physician should exercise clinical judgment based on the symptoms and condition of the individual patient.

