	Grade 3–4	Hold (and consider discontinuation of) cemiplimab when AST or ALT >5.0 times ULN and/or total bilirubin >3.0 times ULN.	
 Consider appropriate consultation and liver biopsy to establish etiology of hepatic injury, if necessary. Treat with high-dose IV glucocorticosteroids for 24–48 hours. When symptoms improve to grade 1 or less, a steroid taper with dexamethasone 4 mg every 4 hours or prednisone at 1–2 mg/kg should be started and continued over no less than 4 weeks. If serum transaminase levels do not decrease 48 hours after initiation of systemic steroids, oral mycophenolate mofetil 500 mg every 12 hours may be given. Infliximab is not recommended due to its potential for hepatotoxicity^b. Several courses of steroid tapering may be necessary as symptoms may worsen when the steroid dose is decreased. 		
Nausea	≤Grade 1	No change in dose	
 Nausea should be treated aggressively, and consideration should be given in subsequent cycles to the administration of prophylactic antiemetic therapy according to standard institutional practice. Patients should be strongly encouraged to maintain liberal oral fluid intake. 		
	Grade 2	Hold until ≤Grade 1. Resume at same dose level. May increase dosing interval by 1 week if it takes more than 4 weeks for toxicities to resolve.			
	Grade 3	Hold until <Grade 2. May increase dosing interval by 1 week for each occurrence. Discontinue if toxicities do not resolve within 12 weeks.			
	Grade 4	Off protocol therapy			

Event(s)	CTCAE v4.03 Grade	Management/ cemiplimab Dosing	Action/Supportive Care Guidelines	Symptoms ^a	Differential Diagnosis
Neutropenia	≤Grade 1	No change in dose	For neutropenia, see general guidelines on hematologic toxicity in Table 2		
	Grade 2	No change in dose			
	Grade 3	No change in dose			
	Grade 4	See Table 2			

Event(s)	CTCAE v4.03 Grade	Management/ cemiplimab Dosing	Action/Supportive Care Guidelines	Symptoms ^a	Differential Diagnosis

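### For Grade 4 immune-related colitis, endocrine, hepatic and unlisted events, the protocol contradicts itself on whether cemiplimab may be resumed

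*Protocol*

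**What the plan says.** Four places in the protocol bear on a Grade 4 nonhematological irAE.

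- **Section 7.3.2, Table 2.** The Grade 4 line of the nonhematological row says to hold, marks restarting criteria and restarting dose as not applicable, and states "Patient must be discontinued". The carve-outs listed in that row ("Note: Exceptions to be treated as for Grade 1 toxicity") are Grade 2 alopecia, Grade 2 fatigue, and clinically insignificant laboratory abnormalities that do not reach AE criteria.
- **Section 7.3.2, body text.** After a treatment-related event, resumption is allowed at the discretion of the investigator and sponsor. The stated exceptions are interruptions longer than 84 days from the previous dose, and uveitis.
- **Section 7.3.2.1, Table 3.** At Grades 3 and 4, treatment is withheld, with this condition: "Discontinue if unable to reduce corticosteroid dose to <10 mg per day prednisone equivalent within 12 weeks of toxicity".
- **Appendix 3.** Event-specific rows. The hepatic row for Grades 3–4, for example, reads "Hold (and consider discontinuation of) cemiplimab when AST or ALT >5.0 times ULN", with a bilirubin criterion alongside.

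The link from Table 2 to the irAE guidance is one sentence, which begins "For additional information regarding AEs with a potential for irAEs" and points to Table 3 and Appendix 3. Section 7.3.2.1 then makes Table 3 the fallback for irAEs that Appendix 3 does not cover, and calls both guidelines subject to clinical judgment.

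**The concern.** A Grade 4 immune-related hepatitis is both a Grade 4 nonhematological toxicity and an irAE, so Table 2 and Appendix 3 both apply to it. Table 2 ends treatment. Appendix 3 holds treatment and leaves discontinuation to be considered. A site that follows either one is following the protocol.

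These are life-threatening events in a study planned at up to approximately 70 sites. If sites resolve the conflict differently, like patients will be managed differently. The reported reasons for stopping treatment will then partly reflect which table was read.

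**Working it through.** No power, alpha or sample-size figure is involved. The check sets the Grade 4 instructions side by side and then looks for text that ranks them.

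**1. Does Table 2 reach irAEs?** Yes. The row covers nonhematological toxicity in general, and none of its three exceptions concerns irAEs or Grade 4.

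**2. What do the irAE sources say at Grade 4?**

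| Source | Grade 4 instruction | Against Table 2 |
|---|---|---|
| Table 3 (irAEs not in Appendix 3) | Withhold; discontinue if steroids cannot be reduced within 12 weeks | Conflicts |
| Appendix 3, colitis, Grades 3–4 | Withhold; same steroid condition | Conflicts |
| Appendix 3, endocrine: thyroid (Grades 3–4) and adrenal/pituitary (Grades 1–4) | Hold until hormone replacement is stable | Conflicts |
| Appendix 3, hepatic, Grades 3–4 | Hold, and consider discontinuation | Conflicts |
| Appendix 3, renal, Grades 3–4 | Dosing column: discontinue. Action column: restart possible | Mixed |
| Appendix 3, uveitis, Grades 3–4 | Discontinue | Agrees |
| Appendix 3, pneumonitis, Grades 3–4 | Discontinue | Agrees |
| Appendix 3, skin, Grade 4 | Permanently discontinue | Agrees |

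Of the seven immune-event classes in Appendix 3, three conflict, three agree and one is mixed. Unlisted irAEs fall to Table 3 and also conflict.

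**3. Is Table 2 ranked against the others?** No. Section 7.3.2.1 puts Appendix 3 ahead of Table 3 but leaves Table 2 out of the order. The linking sentence after Table 2 offers further information and does not replace anything.

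**4. Does the body text settle it?** No. The discretion in Section 7.3.2 to resume lists two exceptions, and Grade 4 nonhematological toxicity is not one of them. Read alone, it permits what Table 2 forbids. The same section requires only a temporary stop for treatment-related toxicity of Grade 3 or higher that the protocol does not otherwise specify. Section 7.3.2.2 lists reasons for permanent discontinuation without naming Grade 4 toxicity, but that list is expressly not exhaustive.

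**5. Are the rows consistent within themselves?** Not all. The renal row is noted above. In the colitis row, the action column permanently discontinues Grade 3 enterocolitis, while the dosing column for Grades 3–4 says withhold.

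**6. Which outputs move?** Disposition (Protocol 10.4.1, SAP 5.4), TEAEs leading to permanent discontinuation (Protocol 10.4.5.1, SAP 5.9.1) and exposure (SAP 5.7). To show how exposure moves, take a patient dosed at 350 mg on days 1, 22 and 43 who then has a Grade 4 event. The SAP takes duration as (last dose − first dose + 21)/7 weeks, and planned intensity as 350/3 = 116.7 mg/week.

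- Stopped for good: duration (42 + 21)/7 = 9 weeks; intensity 1050/9 = 116.7 mg/week; relative dose intensity 1.00.
- Resumed once, 84 days after the previous dose (day 127), assuming for illustration 350 mg: duration (126 + 21)/7 = 21 weeks; intensity 1400/21 = 66.7 mg/week; relative dose intensity 66.7/116.7 = 0.57.

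Only the first version of this patient counts as a discontinuation due to a TEAE.

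**The case against.** The best reply is that the specific rule governs the general one. Directly after Table 2 the protocol sends potential irAEs to Table 3 and Appendix 3, and Section 7.3.2.1 is devoted to irAEs. Appendix 3 also refers back to Table 2 where it wants Table 2 to apply: Grade 4 neutropenia, and Grades 3 and 4 thrombocytopenia. The colitis, endocrine and hepatic rows have no such reference. This is fair evidence of intent, but it remains inference. The back-references also show that the protocol states deference expressly when it means it, and no text exempts irAEs from Table 2.

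Second, Table 2 is itself introduced as guidelines, like Table 3 and Appendix 3. That softens the conflict, yet the Grade 4 cell is worded as an obligation, and the label does not tell a site whether a restart is open.

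Third, the Grade 3 and Grade 4 cells in Table 3 may have been run together when the PDF was read. If the steroid condition belongs to Grade 4 alone, discontinuation there is still conditional, and the colitis row carries the same condition for Grades 3–4.

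Three limiting points stand in full. The hepatic row expressly contemplates discontinuation. Resumption under the body text needs sponsor as well as investigator agreement, so a site does not decide alone. The affected summaries are descriptive.

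**Conclusion.** The contradiction is real and has a definite scope: Grade 4 immune-related colitis, endocrine and hepatic events, and irAEs outside Appendix 3. For these, the protocol both rules out and allows resumption. The renal row needs the same attention because it contradicts itself.

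Three stronger readings are tempting but not supported.

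- A reader might infer that every Grade 4 nonhematological irAE is affected and that no rule can be determined. The uveitis, pneumonitis and skin rows agree with Table 2.
- A reader might infer that some tables let dosing continue through a life-threatening event. In the conflicting rows every source stops dosing at first; only later resumption is in dispute.
- A reader might infer that the primary analysis is compromised. The response-rate hypotheses, sample sizes and exact confidence intervals do not use this rule. Any influence through later exposure would be indirect.

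The number of patients affected cannot be given, because the documents state no expected rate of Grade 4 irAEs. The conclusion assumes that the table cells as extracted carry the published instructions. It takes no position on which clinical rule is right.

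**What to change.** Reconcile the following for Grade 4 irAEs: the nonhematological Grade 4 line of Table 2, the resumption text in Section 7.3.2, Table 3, and the colitis, endocrine, hepatic and renal rows of Appendix 3. Then add one sentence stating which source governs when more than one applies, and place Table 2 explicitly in the order that Section 7.3.2.1 already sets for Appendix 3 and Table 3. The choice of clinical rule belongs to the sponsor and its clinical and safety advisers.

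The cost is amendment wording and site notification. Sample size, analysis methods and the SAP need no change.

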7.3.2.1. Immune-Related Adverse Events

Case report forms (CRFs) for this study are designed to capture AEs that may be suggestive of potential irAEs. Attribution of AEs in the CRFs will require not only the investigator's assessment

regarding whether or not the AE was related to cemiplimab, but also whether or not the AE was an irAE. Please see the CRF completion guidelines for information about attribution of irAEs.

Investigators must be extremely vigilant and be ready to intervene early in the management of irAEs, as the onset of symptoms of irAEs (eg, pneumonitis or endocrinopathies) may be subtle. Detailed guidance of management of irAEs is provided in [Appendix 3](#). In the event of irAEs that are not addressed in [Appendix 3](#), general guidance is provided in [Table 3](#). The recommendations in [Table 3](#) and [Appendix 3](#) should be seen as guidelines, and the treating physician should exercise clinical judgment based on the symptoms and condition of the individual patient.

Table 3: General Treatment Hold Guidelines for Immune-Related Adverse Events

Severity	Withhold/Discontinue Treatment?	Supportive Care
Grade 1	No action	Provide symptomatic treatment
Grade 2	May withhold treatment	Consider systemic corticosteroids in addition to appropriate symptomatic treatment
Grade 3 Grade 4	Withhold treatment Discontinue if unable to reduce corticosteroid dose to <10 mg per day prednisone equivalent within 12 weeks of toxicity	Systemic corticosteroids are indicated in addition to appropriate symptomatic treatment. May utilize 1 to 2 mg/kg prednisone or equivalent per day. Steroid taper should be considered once symptoms improve to Grade 1 or less and tapered over at least 4 weeks. For any severe (Grade 3-4) irAE, if symptoms worsen or do not improve on adequate corticosteroids within 48 to 72 hours, consider adding additional immunosuppressive agents (to be selected from agents such as infliximab, cyclophosphamide, cyclosporine, mycophenolate mofetil). Referral of the patient to a specialized unit for assessment and treatment should be considered.

Note: These recommendations should be seen as guidelines, and the treating physician should exercise clinical judgment based on the symptoms and condition of the individual patient.

Note regarding irAEs: For any AE that is of a type known to be potentially immune-related (eg, rash, colitis, elevated transaminases, endocrine), but is deemed not to be an irAE by the investigator, the sponsor may request additional information.

Based on the emerging safety profile of cemiplimab and other antibodies targeting the PD-1/PD-L1 axis ([Weber 2015](#), [Naidoo 2015](#)), the following working case definitions are provided to help investigators distinguish irAEs from non-immune AEs. These case definitions pertain to the more commonly reported irAEs associated with PD-1 inhibition ([Weber 2015](#), [Naidoo 2015](#)), and is not exhaustive of all possible irAEs. Clinical presentations of less common irAEs, including neurologic, musculoskeletal, cardiac, renal, and ocular events ([Zimmer 2016](#), [Hofmann 2016](#)), should be reviewed in patients with concerning presentations.

The case definitions below have not been validated, and are intended only as guidance for investigators to help distinguish irAEs from non-immune AEs. Investigators' clinical judgment may include other factors when determining immune-relatedness. The case definitions for irAEs may evolve as clinical experience increases with cemiplimab and other antibodies targeting the PD-1/PD-L1 axis.

- a. **Immune-related rash:** Skin examination demonstrates a rash that is usually maculopapular, but other presentations may occur, including papulopustular, follicular, or urticarial dermatitis. Consider dermatologic consultation and biopsy for atypical presentations. Exclude other cause such as virally-induced rash or contact dermatitis.
- b. **Immune-related diarrhea/colitis:** These events are on a continuum, with diarrhea defined as increased stool frequency, and colitis involves abdominal pain and/or radiologic evidence of colonic inflammation (Naidoo 2015). Onset at 4 to 6 weeks is common (Weber 2015). A CT scan usually demonstrates diffuse colitis (Tirumani 2015). Exclude *clostridium difficile* or other infectious etiologies and exclude laxative misuse.
- c. **Immune-related hepatitis:** Laboratory studies are notable for elevated ALT and/or AST that is usually asymptomatic. Viral or other drug-induced hepatitis is excluded. Exclude alcohol-related liver toxicity. If clinically appropriate, consider radiologic imaging to exclude malignant causes. If clinically appropriate, exclude worsening of underlying cirrhosis.
- d. **Immune-related hypothyroidism:** Laboratory studies are notable for elevated TSH associated with low serum free thyroxine (free T4). If elevated TSH is detected, it is recommended that free T4 level also be tested. Elevated TSH with low free T4 establishes the diagnosis of hypothyroidism. Hypothyroidism may be asymptomatic or associated with symptoms such as fatigue, constipation, cold intolerance, dry skin, weight gain, and/or bradycardia. Exclude other causes of hypothyroidism, such as prior radiation therapy to the neck. In patients with prior history of hypothyroidism, exclude noncompliance with thyroid replacement medication.
- e. **Immune-related hyperthyroidism:** Hyperthyroidism should be managed with standard antithyroid pharmacotherapy, and consultation with an endocrinologist is recommended.
- f. **Immune-related pneumonitis:** Pneumonitis, defined as inflammation of the lung parenchyma, may present as shortness of breath, cough, fever, and/or chest pain. Median time from start of anti-PD-1 therapy to onset of pneumonitis is 2.6 months (Nishino 2016), but delayed onset of pneumonitis has been reported. The most common radiologic pattern on CT chest has been described as cryptogenic organizing pneumonia (COP), but other radiographic patterns may occur (Nishino 2016). If performed, biopsy may demonstrate lymphocyte-predominant interstitial pneumonitis with areas of organizing pneumonia (Nishino 2016). Exclude infectious causes of pneumonitis.

Case report forms for irAEs must capture:

- Date of onset and date of resolution. Resolution is defined as improvement to \leq grade 1 and steroid dose \leq 12 mg/day oral prednisone (\leq 10 mg/day methylprednisolone) or equivalent.
- Treatment administered, including specific drugs and doses, duration of immunosuppressive therapy, and if any additional interventions (biopsies, surgical or medical procedures) were required
- Information on dose modifications (eg, date when dose was modified, date dosing was resumed and if reaction occurred with re-challenge)

7.3.2.2. Reasons for Permanent Discontinuation of Study Drug

Reasons for permanent discontinuation of study drug may include, but are not limited to:

- An infusion reaction of grade ≥ 3 severity during or directly following cemiplimab infusion
- Patient withdrawal of consent at any time
- Any medical condition that the investigator or sponsor determines may jeopardize the patient's safety if he or she continues in the study or continues treatment with study drug
- The investigator or sponsor determines it is in the best interest of the patient
- Patients with confirmed disease progression
- Patient noncompliance (eg, not complying with protocol required visits, assessments, and dosing instructions)
- Pregnancy

7.4.1.1. Interruption of the Infusion

The infusion should be interrupted if any of the following AEs are observed:

- cough
- rigors/chills
- rash, pruritus (itching)
- urticaria (hives, welts, wheals)
- diaphoresis (sweating)
- hypotension
- dyspnea (shortness of breath)
- vomiting
- flushing

The reaction(s) should be treated symptomatically, and the infusion may be restarted at 50% of the original rate.

If investigators feel there is a medical need for treatment or discontinuation of the infusion other than described above, they should use clinical judgment to provide the appropriate response according to typical clinical practice.

For patients who experience infusion-related hypersensitivity reactions that are less than grade 3 and who plan to continue treatment, premedication will be required for retreatment.

For grade 1 symptoms (mild reaction; infusion interruption not indicated; intervention not indicated), the following prophylactic medications are recommended for future infusions: diphenhydramine 50 mg (or equivalent) and/or acetaminophen/paracetamol 325 mg to 1000 mg at least 30 minutes prior to subsequent cemiplimab infusions.

For grade 2 symptoms (moderate reaction that requires therapy or infusion interruption, but for which symptoms resolve promptly with appropriate treatment such as antihistamines, nonsteroidal anti-inflammatory drugs, narcotics, corticosteroids, and/or IV fluids; prophylactic medications indicated ≤ 24 hours), the following prophylactic medications are recommended for future infusions: diphenhydramine 50 mg (or equivalent) and/or acetaminophen/paracetamol 325 mg to 1000 mg at least 30 minutes prior to subsequent cemiplimab infusions. If necessary, corticosteroids (up to 25 mg of hydrocortisone or equivalent) may be used.

